12.9 Analysis of Laboratory Correlative Studies

For the laboratory correlative studies, patients who receive at least one GVAX/placebo vaccination will be included. To identify and determine relevance of vaccine induced immune responses, we will compare the laboratory parameters described in Section 8.0 between the GVAX and placebo arm. The general overview of the analysis is that all longitudinal measurements will be graphically assessed and simple comparison will be made at each time point using either Fisher's exact test for categorical variables or Wilcoxon-Rank-Sum test for continuous variables without considering multiple testing. For long term responders, repeated measures analysis will be performed to characterize the pattern of each immunologic/biologic response. If there appears to be association between these measurements and PFS, we will incorporate these measurements as time dependent repeated covariates in time-toevent model and/or explore a joint model of longitudinal and survival data²⁶. When data are available, we will first validate the previous finding of elevated shed MICA, a NKG2D ligand. In the previous report of GVAX (DFCI#04023), the median soluble MICA level (sMICA) among 7 long-term responders was 1,947 pg/ml before HCT, but fell to 383 pg/ml within 1 year post HCT. In contrast, no marked decrease was seen among 34 control patients. Conservatively extrapolating this result, if the average percent reduction in sMICA level from pre to 1 year post randomization in the GVAX arm is 70% and 10% in the placebo arm, we will have 85% power to detect a 60% difference, assuming the standard deviation of the difference is 60% (i.e., effect size=1). This power calculation is based on asymptotic power of the Wilcoxon-Rank-Sum test and assumes a sample size of 25 in the GVAX arm and 16 in the placebo arm at 1-year post randomization.

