8.0 CORRELATIVE/SPECIAL STUDIES

Biologic responses to vaccination following allogeneic stem cell transplant will be assessed by laboratory and histologic analyses of blood before and after vaccination, and skin biopsy samples at vaccination. Bone marrow aspirates will also be cryopreserved, if sufficient material is available. We anticipate that vaccination will elicit robust infiltrates composed of dendritic cells, macrophages, granulocytes, and lymphocytes. The numbers and proportions of CD4+ and CD8+ T effectors and FoxP3+ Tregs will be evaluated. The local production of relevant cytokines and chemokines will also be examined using real-time PCR and commercially available RNase protection assays.

Serum and circulating mononuclear cells will be frozen prior to beginning vaccination and at regular intervals thereafter. These longitudinal samples will be analyzed for immune cell numbers and subsets. We will use multicolor flow cytometry methods (5 or 9 color), already established in the Cancer Vaccine Center Immune Assessment Core, to investigate immune cell subsets. These phenotypic measurements will be complemented with functional studies. An evaluation of T cell proliferation, cytokine production, and cytotoxicity will be undertaken, employing autologous tumors as targets, when available. The samples will also be used in research studies aimed at identifying the target antigens of vaccination, characterizing NK, T and B cell responses to these targets, and delineating the mechanisms involved in protective immunity. These research tests may include evaluation of reactivity to targets identified in earlier vaccine studies; these may include ATP6S1, melanoma-inhibitor of apoptosis protein (ML-IAP), opioid growth factor receptor (OGFr), CML28, CML66, PDI, ERp5, L1CAM, angiopoietin-1/2, MIF, progranulin, and MICA.

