12.8 Statistical Analysis Plan

The primary analysis will be the modified ITT analysis for the primary endpoint of PFS at 18 months after randomization. The primary analysis will be performed using the Kaplan-Meier estimates for PFS for each arm at 18 months along with 95% confidence intervals. Several secondary analyses of PFS will be conducted, depending on an assessment of the original assumption of non-proportional hazards assumed in the study design. First of all, graphical and analytical diagnostics will be used to assess the presence of non-proportional hazards between treatment arms. If there is no evidence of nonproportional hazards, a relative risk will be estimated from the Cox model both unadjusted and adjusted for other covariates. To assess the effect of GVAX, several approaches will be taken: 1) inclusion of the treatment arm as a fixed covariate in a model, 2) inclusion of the total number of GVAX vaccinations (0-6) as a fixed covariate in a model, 3) treating the number of GVAX/placebo vaccinations as a time dependent repeated measures and an interaction between the number of vaccinations and the treatment arm in a model, 4) exploring a joint model for survival and longitudinal data. 26 If there appears to be non-proportional hazards, several analyses will be conducted: 1) a comparison of PFS at 18 months post randomization will be conducted using the linear combination test proposed by Logan et al.^{24, 28.29} This method directly compares the PFS curves starting at 18 months, and accounts for patients enrolled early in the study having additional follow-up past 18 months. 2) a pseudo value regression approach³⁰, 3) PFS from the start of vaccination will be analyzed, 4) multivariable cure rate model will be performed as described in Ibrahim et al.²⁷

Secondary objectives include relapse and non-relapse mortality (NRM), acute and chronic GVHD, overall survival. For the comparison of GVHD, NRM and relapse, we will perform competing risks data analysis using Gray test and competing risks regression analysis.²⁵ All laboratory correlative studies will be analyzed using appropriate statistical methods. In particular, the effect of vaccination on infiltration of dendritic cells, macrophages, granulocytes, and lymphocytes as well as T cell reconstitution will be examined by comparing pre to post vaccination data and the GVAX to the

placebo arm.

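### Section 12.9 does not say how the pre-vaccination value enters the between-arm marker tests, and plans no model of the arm effect over time in all vaccinated patients

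*Combined protocol and SAP*

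**What the plan says.** Objective 1.3(f) is to compare the biologic activity of GVAX with that of placebo. Section 12.9 sets the general method. The population is broad: "patients who receive at least one GVAX/placebo vaccination will be included". For the arms, "simple comparison will be made at each time point using either Fisher's exact test" for categorical markers or a "Wilcoxon-Rank-Sum test for continuous variables without considering multiple testing". No baseline covariate or change score is named for these tests.

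The same section gives repeated measures a narrower role: "For long term responders, repeated measures analysis will be performed to characterize the pattern of each immunologic/biologic response". It then adds a conditional step: "If there appears to be association between these measurements and PFS, we will incorporate these measurements as time dependent repeated covariates" in a time-to-event model, with a joint longitudinal-survival model as a further or alternative option.

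Pre-vaccination data exist and are used in places. Section 8.0 states: "Serum and circulating mononuclear cells will be frozen prior to beginning vaccination and at regular intervals thereafter". The Study Calendar (9.0) lists immune bloods at enrollment, day 20-30 post SCT and vaccine 1. Section 12.8 says that cellular infiltration and T cell reconstitution "will be examined by comparing pre to post vaccination data and the GVAX to the" placebo arm. The one powered marker comparison in 12.9, soluble MICA, is expressed as percent reduction from pre to 1 year.

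**The concern.** Immune recovery after transplant is likely to differ widely between patients. If each visit is tested on its own without using the patient's own starting value, those differences stay in the error term. The text leaves this open: an analyst could test levels, changes or adjusted values, and could choose any of three draws as the baseline. That choice affects power, and it could be made after the data are seen.

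The one analysis named as repeated measures is confined to long-term responders. That group is formed by what happens after randomization, so a GVAX-placebo contrast inside it is not a randomized comparison. The time-dependent and joint models ask whether a marker goes with PFS, not what the vaccine did to the marker.

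Finally, 12.9 aims to identify vaccine-induced responses, and many nominal p-values with no summary of multiplicity make chance findings hard to recognise. At stake is the reading of a secondary objective, not the efficacy result.

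**Working it through.** **1. The plan's own figure.** Inputs from 12.9: 25 versus 16 patients, difference 60%, SD 60% (effect size 1), Wilcoxon test, stated power 85%. Alpha is not given there; two-sided 0.05 is assumed.

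- SE in SD units = √(1/25 + 1/16) = √0.1025 = 0.320.
- Asymptotic Wilcoxon power = Φ(√(3/π) × 1/0.320 − 1.96) = Φ(1.09) = 0.863.
- Using the Mann-Whitney variance under the alternative gives 0.842; a simulation of 40,000 runs gives 0.839.

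The stated 85% is reproduced. This comparison already refers to a pre value.

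**2. Where 25 and 16 may come from.** From the design curves in 12.5 at 12 months, S_A = 0.482 and S_B = 0.311. With 53 per arm (12.2), 53 × 0.482 = 25.5 and 53 × 0.311 = 16.5. The 1-year comparison therefore appears to be sized on patients still progression-free. This agrees with 5.3.6, which ends study testing after relapse that needs further therapy or hospice. Late visits are thus conditional on remaining on study visits, whatever model is used.

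**3. Precision.** The documents give no pre/post correlation r, so a range is assumed. With equal variance σ² before and after:

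- unadjusted level: σ²
- change score: 2σ²(1 − r)
- baseline-adjusted: σ²(1 − r²)

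The adjusted variance is 1 − r² of the level variance and (1 + r)/2 of the change-score variance. The power columns take 25 versus 16, an illustrative arm effect of 0.6 SD on the follow-up value, and two-sided 0.05.

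| r (assumed) | Variance cut vs level | Equivalent extra patients vs level | Variance ratio vs change | Power: level, Wilcoxon | Power: change, Wilcoxon | Power: adjusted |
|---|---|---|---|---|---|---|
| 0.3 | 9% | 10% | 0.65 | 0.449 | 0.340 | 0.502 |
| 0.5 | 25% | 33% | 0.75 | 0.449 | 0.449 | 0.581 |
| 0.7 | 49% | 96% | 0.85 | 0.449 | 0.657 | 0.747 |

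A small part of the power gap comes from the Wilcoxon efficiency factor: at r = 0 the adjusted analysis has 0.466 against 0.449. Change scores do worse than levels when r is below 0.5. Adjustment does not lose to either at any r shown. At r = 0.7 its gain over a change score equals 1/0.85 − 1 = 18% more patients.

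**4. Number of tests.** Section 8.0 names 12 optional targets, or 13 if angiopoietin-1 and -2 are counted separately. Post-baseline draws in the Study Calendar: about 2 during vaccination, 1 a month after the last vaccine, then 6, 9, 12 and 18 months, about 7 in all.

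- 12 × 7 = 84 tests; 84 × 0.05 = 4.2 expected false positives under the null.
- 13 × 7 = 91 tests; 91 × 0.05 = 4.55, about 4.6.
- With one contrast per target: 12 × 0.05 = 0.6 to 13 × 0.05 = 0.65.

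These expectations hold even if the tests are correlated. They assume that every target is assayed at every draw.

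**The case against.** The strongest reply is that this is openly exploratory work, described as a general overview, with the absence of multiplicity control stated and no stopping or efficacy decision resting on it. That stands, and it limits the weight of the point.

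Several stronger readings are tempting and are not supported:

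- A reader might infer that the plan ignores its pre-vaccination samples. It does not. Section 12.8 plans pre-to-post comparisons, and the soluble MICA comparison is a reduction from pre.
- A reader might infer that raw levels are tested at each visit. The text does not say so; it is silent on level or change.
- A reader might infer that longitudinal modelling is confined to responders. The time-dependent and joint models are not, though they depend on an apparent association with PFS and answer a different question.
- A reader might infer that an arm effect will be claimed among responders. The stated purpose is only to describe pattern.
- A reader might infer that four or five false targets will be reported. Section 8.0 makes both the tests and the target list optional, and 12.9 states no alpha.

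It is also fair to say that the gain over a change score can be much smaller than over a level (18% against 96% in equivalent patients at r = 0.7), and that a longitudinal model does not remove selection by relapse at late visits.

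The gap remains: the role and definition of baseline in the general between-arm test are unspecified, and no all-patient model of the arm effect is planned.

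**Conclusion.** The concern holds in this limited form. For objective 1.3(f), 12.9 leaves the use of baseline open in its per-visit tests and names repeated measures only for an outcome-defined group. Adjusting for samples the trial already draws would lower residual variance by 9% to 49% against an unadjusted level for r from 0.3 to 0.7, and by 35% to 15% against a change score over the same range. These sizes rest on assumed correlations and on equal variance before and after. The count of 4.2 to 4.6 chance findings rests on all optional assays being run at all seven draws, an assumed 0.05 level and no vaccine effect. The change is worth making because it costs little. The primary PFS analysis is unaffected.

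**What to change.** Amend 12.9 as follows:

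- **Model.** For each continuous blood marker, make the between-arm analysis a longitudinal model on the log or rank scale in all patients with at least one vaccination. Include arm, visit, arm-by-visit and the pre-vaccination value as covariate. Name the draw or draws that define that value, and one visit or contrast that supplies the p-value.
- **Categorical markers.** Keep Fisher's exact test.
- **Soluble MICA.** Keep the comparison from the pre-HCT baseline as a separate analysis, since that is the finding to be validated.
- **Responders.** Label this analysis descriptive, with no inference between arms.
- **Late visits.** State that they are conditional on remaining on study visits, because testing stops under 5.3.6.
- **Multiplicity.** Report Benjamini-Hochberg q-values for the one named contrast across the targets actually assayed, beside the nominal p-values.

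The cost is SAP wording and modest extra analysis, with no new samples. The small downside is that fewer markers will be reported as nominally significant.

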1.1 Study Design

GVAX vaccines will be generated by adenoviral vector mediated GM-CSF gene transfer into myeloblasts harvested from study subjects prior to admission for hematopoietic stem cell transplant Patients with Myelodysplastic syndromes (MDS) with excess marrow blasts or Acute myeloid leukemia (AML) not in remission are eligible. Leukemia cells will be harvested for vaccination generation after enrollment. Patients will be randomized (1:1) to GVAX versus placebo arm prior to The assignment of treatment arm will be blinded to the patients, treating transplant admission. physicians, nurses, research staff, and data assessors. Between the leukemia cell harvest and admission for allogeneic HSCT, patients are allowed to receive additional therapy (e.g. HMA therapy, chemotherapy etc.) at the discretion of the treating physician. Between day+30 to +60* after HSCT, patients with adequate hematologic recovery and no GVHD requiring systemic therapy will receive GVAX or placebo vaccine (normal saline) injections weekly x 3 week, then starting on week 5, every 2 weeks for 6 weeks, to complete a set of six total vaccinations. Patients will remain on tacrolimus for GVHD prevention during the vaccination period. Tacrolimus taper may commence after completion of vaccination, at the discretion of the treating physician, with the goal to be off immune suppression by 6-9 months post transplant in the absence of GVHD.

* Day 60 or next business day, if day 60 occurs on a weekend or holiday

1.2 **Primary Objective:**

Progression-free survival (PFS) at 18 months after randomization

1.3 Secondary Objectives:

- a) To assess the safety of vaccination following allogeneic (ablative or reduced intensity) stem cell transplantation
- b) To assess incidence of grade 2-4 and grade 3-4 acute GVHD, and chronic GVHD after vaccination following allogeneic stem cell transplantation.
- c) To assess PFS after start of vaccination
- d) To assess relapse and non-relapse mortality after vaccination
- e) To assess overall survival after vaccination
- f) To assess biologic activity of GVAX as compared to placebo vaccination after HSCT (see Section 8.0)

CONFIDENTIAL

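### Section 12.9 tests each immune marker between arms at each time point with no multiplicity control and no exploratory label, so chance hits can be reported as vaccine-induced responses

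*Combined protocol and SAP*

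**What the plan says.** Section 1.3(f) makes it a secondary objective "To assess biologic activity of GVAX as compared to placebo vaccination after HSCT", and Section 12.1.2.2 lists biologic responses as a secondary endpoint. Section 12.9 holds the detailed analysis. Its purpose is given as "To identify and determine relevance of vaccine induced immune responses", and its between-arm method is that a "simple comparison will be made at each time point", by Fisher's exact test for categorical variables or the "Wilcoxon-Rank-Sum test for continuous variables without considering multiple testing" for continuous ones.

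The parameters come from Section 8.0. Besides cell subsets, cytokines and functional assays, it lists earlier vaccine targets: "these may include ATP6S1, melanoma-inhibitor of apoptosis protein (ML-IAP), opioid growth factor receptor (OGFr), CML28, CML66, PDI, ERp5, L1CAM, angiopoietin-1/2, MIF, progranulin, and MICA". That is 12 entries, in an open list.

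Section 12.9 also says that soluble MICA will be examined first. It gives that marker its own power statement: 85% power for a 60-point difference in percent reduction from pre to 1 year post randomization, with SD 60%, 25 GVAX and 16 placebo patients. No level or sidedness is given for this test or for any other correlative test.

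**The concern.** The text gives these comparisons an identifying purpose and at the same time sets multiplicity aside. A family of many markers at many visits will usually produce some p-values below 0.05 even when the vaccine does nothing. Nothing in 12.9 says how many hits, at which visit or at what level, would count as a vaccine-induced response, and nothing labels the results hypothesis-generating. A reader of the final report would be unable to tell a chance hit from a real one. What is at stake is the credibility of secondary objective 1.3(f).

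**Working it through.** **1. Reproduce the plan's own figure.** Inputs from 12.9: effect size 60/60 = 1, n = 25 and 16. With the Wilcoxon asymptotic relative efficiency 3/π and an assumed two-sided 0.05:

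power = Φ(√[(25 × 16/41) × 3/π] − 1.96) = Φ(√9.316 − 1.96) = Φ(1.092) = 86%.

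This is close to the stated 85%. Simulation gives 84%, Noether's formula 80%, and a one-sided 0.05 gives 92%. Two-sided 0.05 is therefore a reasonable reading, but it remains an assumption.

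**2. Count the family.** Markers: the 12 targets in Section 8.0. Times: the Section 9.0 calendar has blood draws monthly during vaccination (about 2), 1 month after the last vaccine, and at 6, 9, 12 and 18 months post SCT, so 2 + 1 + 4 = 7. Tests: 12 × 7 = 84. The cell subsets, cytokines, functional assays and biopsy infiltrates are not counted.

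**3. Independent tests under no effect.**
- P(at least one p < 0.05) = 1 − 0.95^84 = 98.7%.
- Expected chance hits = 84 × 0.05 = 4.2. Correlation does not change this expectation.

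**4. Allow for correlation.** Repeated measures of related markers in the same patients are correlated, so null Wilcoxon tests were simulated. One set takes per-arm numbers from the 12.5 curves:
- at 2.5 months, 53 × S_A = 53 × 0.743 = 39 and 53 × S_B = 53 × 0.703 = 37;
- at 18 months, 53 × 0.459 = 24 and 53 × 0.261 = 14.

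The other set holds 25 v 16 at every visit. The table gives P(at least one p < 0.05), with 1,000 trials per cell in the first column and 1,500 in the others.

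| Correlation across times / across markers | 12 × 7, n from 12.5 curves | 12 × 7, n = 25 v 16 | 12 × 5, n = 25 v 16 |
|---|---|---|---|
| 0 / 0 | 0.98 | 0.98 | 0.95 |
| 0.5 / 0.3 | 0.94 | 0.93 | 0.86 |
| 0.5 / 0.5 | 0.89 | 0.89 | 0.80 |
| 0.8 / 0.5 | 0.81 | 0.73 | 0.65 |
| 0.8 / 0.8 | 0.58 | 0.49 | 0.44 |

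For 12 markers the range is thus roughly 45 to 99%. The lowest value is for 5 draws at correlation 0.8/0.8.

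**5. Binary markers.** Reactivity to a target may be recorded as yes or no and tested by Fisher's exact test, which is conservative. Repeating the 12 × 7 null simulation with Fisher's test at assumed positivity of 5 to 50% gives 0.35 to 0.93 for at least one hit and 0.8 to 3.0 expected chance hits.

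**6. Effect of the remedy.** Benjamini-Hochberg at 10% over the 84 continuous tests leaves about a 5 to 10% chance of any false call. Keeping soluble MICA at 1 year as a single two-sided 0.05 test retains the 86% power. Putting it under Bonferroni would cut its power to 57% (12 tests) or 35% (84 tests).

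**The case against.** The strongest reply is that this is openly declared, unadjusted correlative work in a phase II trial. Section 12.5 calls the comparison nondefinitive and accepts a one-sided 0.15 for the primary test. Section 12.9 describes the tests only as an overview ("The general overview of the analysis is that all longitudinal measurements will be graphically assessed"), adds repeated-measures analysis, and already gives one marker priority with a direction, a time point and a sample size. Section 8.0 commits to no fixed family: "These research tests may include evaluation of reactivity to targets identified in earlier vaccine studies". All of this stands, and it limits the point to a reporting improvement. Disclosure alone, however, does not help a reader interpret several expected chance hits in a section meant to identify responses.

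Four stronger readings are tempting, and the documents do not support them.

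- **An inert vaccine would be declared active.** Section 12.9 has no rule that one significant test establishes biologic activity. The computed probability is that of at least one nominal hit, not of a declaration.
- **The chance of a false hit is near certainty.** The 98.7% needs independence, a 0.05 level and 84 tests, none of which is stated. Twelve independent tests give 1 − 0.95^12 = 46%. Counting only one pre-named direction in the 12 × 7 family gives 26 to 87%.
- **Chance hits would be carried into the PFS models.** Section 12.9 admits measurements to those models when they appear associated with PFS, not when the arms differ.
- **Soluble MICA can simply be kept at its stated level.** No level is stated, so one has to be added.

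**Conclusion.** The point holds as a cheap improvement. Section 12.9 prescribes unadjusted marker-by-visit testing for a secondary objective, without an exploratory label or a criterion for calling a response vaccine-induced. With 12 continuous markers at 5 to 7 draws and an assumed two-sided 0.05, at least one chance difference would appear in roughly 45 to 99% of trials of an inert vaccine. About 4 such hits are expected at 7 draws. The figures rest on the assumed level, on the open target list being tested in full, and on the correlations tried. Fewer markers, or many binary ones, would lower them. The primary PFS conclusion is not touched.

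**What to change.** In 12.9, replace the clause that sets multiplicity aside with the following:

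1. The change in soluble MICA from pre to 1 year is the single key test of biologic activity. State its level (two-sided 0.05 approximately reproduces the stated power) and name the calendar visits that supply the two measurements.
2. For every other marker-by-time comparison, report Benjamini-Hochberg q-values across the whole family beside the raw p-values.
3. Call a response vaccine-induced only if it meets a pre-stated false discovery rate, for example 10%. Label other nominal hits hypothesis-generating.
4. Fix the marker list and visits that form the family before unblinding.

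The cost is a few sentences in the plan and a line of code, with no change to samples, visits or assays. The 10% is a choice for the study team. The downside is lower sensitivity to weak single-marker signals, which remain visible in the raw p-values.
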